### **Plans for Assuring Compliance with Requirements Regarding the Reporting of Adverse Events (AE)**

For trials monitored by the NCI's Clinical Data Update System (CDUS), adverse event information is transmitted electronically to NCI on a quarterly basis. For trials monitored by NCI's Clinical Trials Monitoring Service (CTMS), adverse event information is transmitted electronically to NCI every two weeks.

The Protocol Chair, AMC Group Chair, and the AMC ODMC share responsibility in assuring that participating investigators comply with the protocol requirements for adverse event reporting. All AMC investigators certify compliance with NCI and FDA requirements for adverse event reporting by signing the AMC Adherence Statement for site membership, the protocol signature page for each protocol active at the site, and Form FDA-1572 for CTEP investigator registration and IND studies sponsored by AMC investigators. Investigators are responsible for identifying and reporting all adverse events to the AMC ODMC, CTEP-AERS, and/or sponsors according to the protocol requirements, and assuring compliance with reporting to the local IRB. Protocol

compliance with adverse event reporting requirements is assessed by the AMC ODMC during routine site monitoring visits by reviewing the site's source documentation.

The data entry system used for AMC studies, AdvantageEDCSM (a web-based data entry and enrollment system), is programmed to notify the site investigator, protocol chair, and AMC ODMC via email in the event that a site reports an adverse event that meets expedited reporting criteria to NCI and/or FDA. If the site does not follow with a CTEP-AERS report, the AMC ODMC contacts sites to request an expedited report. Additionally, the protocol chair, AMC ODMC, and the AMC Medical Monitor review reported adverse events on a routine basis to identify adverse events reported by sites that require expedited reporting via CTEP-AERS. The Protocol Chair, AMC Group Chair, and IND sponsors have general oversight for assuring that routine and expedited adverse reporting requirements are met by the responsible parties.

**Plans for Assuring that any Action Resulting in a Temporary or Permanent Suspension of an NCI-Funded Clinical Trial is Reported to the NCI Grant Program Director Responsible for the Grant**

In the event that termination of the trial or major modification to the protocol is under consideration, the Protocol Chair will convene the AMC Data Coordinator and Disease-oriented Working Group Chair by conference call to discuss the options. For phase I and II trials, the Protocol Chair also has the option of asking the AMC DSMB to review the study. The AMC ODMC will inform the CTEP Protocol Information Office (PIO) when studies are temporarily or permanently closed. The Cancer Treatment and Evaluation Program (CTEP) of the National Cancer Institute (NCI) must approve all protocol amendments prior to distributing to the AMC sites.

**Plans for Assuring Data Accuracy and Protocol Compliance**

All study data for AMC clinical trials are entered directly by AMC site staff into AdvantageEDCSM. During data entry, the system performs validation checks on many fields and performs consistency checks between select fields. Range checks are placed on each field to eliminate entry of out-of-range values. Edit check programs are run on the database on a set schedule to identify and resolve inconsistencies between forms or data collected at different points in time. AMC ODMC staff routinely interacts with site staff to resolve any data problems.

In accordance with NCI guidelines, the AMC ODMC conducts monitoring visits at the AMC sites to evaluate compliance with regulatory issues, and to review data for specific cases by checking source documents. These reports are sent to the site Principal Investigator and to the NCI. In the event that major violations are identified, sites are asked to provide a plan to correct deficiencies within 30 days. If needed, a repeat site visit is conducted. In the event that a site does not correct deficiencies in a pre-determined time frame, the AMC Executive Committee has the option of taking action against the site. Possible actions include, but are not limited to, suspending enrollment of new participants to AMC trials until deficiencies are corrected; recommending a decrease in funding to the site; and requiring specific training for site investigators or staff members.

## APPENDIX VI: AIDS AND CANCER SPECIMEN RESOURCE (ACSR) SPECIMEN PREPARATION AND SHIPPING INSTRUCTIONS

### A. GENERAL

To ship blood specimens, use a diagnostic shipper approved for a volume of at least 30 cc. The use of the SAF-T-PAK STP 210 diagnostic cardboard shipper is recommended. These shippers may be ordered at the SAF-T-PAK website [www.saftpak.com](http://www.saftpak.com). The following instructions below are for use with the recommended STP-210 shipper. If using another federally approved diagnostic shipper, please follow instructions provided for that specific shipper.

**NOTE:** Specimens MUST BE SHIPPED **Monday** through **Thursday** as an **OVERNIGHT PRIORITY** shipment. Specimens are **NOT ACCEPTED ON SATURDAYS OR SUNDAYS** in the GWU/ACSR Lab.

### B. SPECIMEN PREPARATION, PACKAGING, AND SHIPMENT

#### *Blood specimens*

Draw two 8.5 cc (ml) yellow top [acid citrate dextrose (ACD) solution A] tubes from study participant. With a black, water resistant, sharpie pen, label each specimen with the following information:

1. AMC Protocol #087
2. AMC Participant ID#
3. Date and time of collection
4. Specimen type, i.e., WB=Whole Blood, P=Plasma, S=Serum, or Tissue
5. Specimen purpose: Donation

#### *Specimen shipment*

1. Seal the tops of the two 8.5 cc yellow tops with parafilm.
2. Place the two sealed tubes into bubble wrap (provided in STP-210 kit).
3. Tape around the bubble wrap so that the roll stays together and the tubes cannot fall out or break.
4. Place absorbent material sheet around the bubble wrapped tubes and slip into a biohazard poly-bag and “self-seal.”
5. Place poly-bag containing tubes into the white TYVEK bag and seal.
6. Place the TYVEK bag into the STP-210 diagnostic cardboard shipper. Seal the cardboard shipper with clear packing/shipping tape.
7. Affix the FED-EX airbill on blank side of the shipper making sure that it is marked “FED-EX PRIORITY OVERNIGHT.”
8. Mark “OTHER” in the airbill under “Packaging.” Please use FedEx #: **352207845**.
9. Under airbill section “Special Handling” indicate “YES-SHIPPERS DECLARATION NOT REQUIRED.”
10. Place “From/To” information onto areas provided on the shipper.

**Blood specimens** should be shipped by overnight express at room temperature to:

[name]  
George Washington University Medical Center  
[name]  
[name]  
[name]  
[contact]  
[contact]  
Email: [[contact]](mailto:[contact])  
[[contact]](mailto:[contact])

11. Make certain that shipper is already either pre-labeled with the “UN#3373” stamp, or make a paper label with “UN#3373” and affix it to the shipper.
12. Make certain that the net volume of the specimen being shipped is written in the space provided on the shipper or make a separate label with the volume in ml and affix to the shipper.
13. Affix airbill to shipper so that the ‘UN’ and ‘VOLUME’ labels are visible.
14. RETAIN THE TOP COPY OF THE AIRWAY BILL FOR YOUR RECORDS.
15. Place the box in the FedEx pickup area at your site or call to request a package pickup.

**Please Note:** The shippers will be mailed back to each AMC site.

INSTRUCTIONS FOR BLOOD SPECIMENS COLLECTED ON THURSDAY AND FRIDAY:

#### **C. PREPARATION OF PLASMA AND MONONUCLEAR CELLS**

It is preferable that separation occurs as soon as possible. If necessary, whole blood in ACD (yellow top tubes) can be held at room temperature for no more than 24 hours. Plasma and PBMC should be separated according to the AMC Biorepository’s SOP on Separation of Plasma and Mononuclear Cells, available on the AMC Operations web site.

Freeze the cell suspension in 0.5 ml aliquots in sterile NUNC vials by placing the NUNC tubes in a room temperature, alcohol saturated, control rate freezer container and store in the -80°C freezer overnight. Transfer the cell suspension into the liquid nitrogen temperature freezer for long-term storage the next working day.

**\*\*\*PLEASE DOUBLE CHECK PACKAGING OF SHIPPER AND DO NOT DEVIATE FROM REQUESTED LABELING.** Shipping frozen aliquots requires the use of packaging acceptable for dry ice and Class 9 label with weight of dry ice written on package.

#### **D. PREPARATION OF TISSUE SAMPLES**

Tissue specimens to be fresh frozen should be placed in OCT and then on dry ice immediately. The specimens may stay on dry ice until being transferred to a -80°C freezer.

Tissue specimens for donation may be batched for shipping after storage in -80°C freezer. Allowable shipment days are Monday through Thursday. Shipping frozen tissue requires the use of packaging acceptable for dry ice and Class 9 label with weight of dry ice written on package.

**TISSUE** specimens should be shipped by overnight express to:

[name]  
George Washington University Medical Center  
[name]  
Room 202  
[name]  
[contact]  
[contact]

#### **E. RECORD OF SPECIMENS**

This study will track specimens via GlobalTraceSM, a component of the AMC AdvantageEDCSM system. The GlobalTraceSM shipment manifest must accompany all specimen shipments.

## APPENDIX VIII: PARTICIPANT MEDICATION DIARY/CALENDAR

AMC Protocol # \_\_\_\_\_

### PARTICIPANT'S MEDICATION DIARY – **CABOZANTINIB**

Today's date \_\_\_\_\_ Agent \_\_\_\_\_ Cabozantinib \_\_\_\_\_

Participant Name \_\_\_\_\_ (initials acceptable) Participant Study ID \_\_\_\_\_

#### INSTRUCTIONS TO THE PARTICIPANT:

1. Complete one form for each 4 week-period while you take **cabozantinib**.
2. You will take your dose of **cabozantinib** each day in the morning for 4 weeks. You will take \_\_\_\_\_ 20 mg tablets and \_\_\_\_\_ 60 mg tablets every morning. DO NOT MAKE UP ANY MISSED DOSE, just wait until the next day before taking the next dose.
3. Medication must be taken on an empty stomach. Participants must fast for 2 hours before and 1 hour following each dose of cabozantinib.
4. Wash hands immediately after touching the tablet(s).
5. Record the date, the number of tablets of each size you took, and when you took them.
6. If you have any comments or notice any side effects, please record them in the Comments column.
7. Please return this form to your physician when you go for your next appointment.

Day	Date	Time of daily dose	Check (✓) if taken on empty stomach (see instruction #3).	# of tablets taken		Comments
				20 mg	60 mg	
1						
2						
3						
4						
5						
6						
7						
8						
9						

10						
11						
12						
13						
14						
15						
16						
17						
18						
19						
20						
21						
22						
23						
24						
25						
26						
27						
28						

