## 5.0 TREATMENT PLAN

### 5.1 Agent Administration

Treatment will be administered on an outpatient basis. Reported adverse events and potential risks are described in [Section 7.0](#). Appropriate dose modifications are described in [Section 6.0](#). No investigational or commercial agents or therapies other than those described below may be administered with the intent to treat the participant's malignancy.

Cabozantinib will be administered orally as once daily doses continuously over 28 day cycles in each of three treatment strata in participant cohorts as detailed in the table below. The starting dose in each treatment Stratum will be Dose Level 1. Dose escalation will proceed in participant cohorts within each Stratum according to the scheme described in [Section 5.2](#).

**NOTES: The participant will be requested to maintain a medication diary of each dose of medication. The medication diary will be returned to clinic staff at the end of each course.**

**The site will be required to document study agent return by participant in source documents. Non-compliance with study agent administration should be noted at the time of diary collection and the participant should be instructed again regarding dosing instructions.**

**Missed cabozantinib doses will NOT be made up. Participants who have missed a dose should wait until the next scheduled dose to resume therapy.**

For Stratum A, one dose de-escalation cohort (Dose Level -1) will be permitted for excessive toxicity observed at the initial (Dose Level 1) cohort. For Stratum B and Stratum C, two dose de-escalation cohorts (up to Dose Level -2) will be permitted for toxicity observed at initial cohorts.

For participants treated on Stratum A no dose escalation will proceed beyond Dose Level 3 (60 mg). For participants treated on Stratum B, no dose escalation will proceed beyond Dose Level 2 (100 mg). For participants treated on Stratum C, no dose escalation will proceed beyond Dose Level 1.

Dose Escalation Schedule			
Dose Level	Dose of Cabozantinib (XL184)*		
	Stratum A ART Regimens Including Drugs that Inhibit CYP3A4 A (mg/day)	Stratum B ART Regimens Including Drugs that Induce CYP3A4 B (mg/day)	Stratum C All Other ART Regimens C (mg/day)
Level -2	-	20	20
Level -1	20 mg every other day	40	40
Level 1	20	60	60
Level 2	40	100	-
Level 3	60	-	-

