#### **5.4 Duration of Therapy**

In the absence of treatment delays due to adverse event(s), treatment may continue until one of the following criteria applies:

- Disease progression,
- Intercurrent illness that prevents further administration of treatment,
- Dose-limiting toxicity (DLT requiring discontinuation of therapy, as defined in [Section 5.2](#)). Dose reductions in the first cycle of therapy for cabozantinib-related adverse events are permitted.
- Other unacceptable adverse event(s),
- Treatment delay of 14 days or greater during Cycle 1 due to unresolved toxicity (DLT definition, [Section 5.2](#)).
- Treatment delay in subsequent cycles > 6 weeks due to toxicity (treatment delays for other reasons may be permitted at the discretion of the Study Chairs),
- Participant decides to withdraw from the study.
- General or specific changes in the participant's condition render the participant unacceptable for further treatment in the judgment of the investigator, including:
  - Necessity for treatment with other anticancer treatment prohibited by the protocol.
  - Change to a ritonavir or cobicistat-containing antiretroviral regimen for a participant enrolled on a different study arm (see [Section 5.3.1.2](#)).
  - Sexually active participants who refuse to use medically accepted barrier methods of contraception (e.g., male condom, female condom) during the course of the study and for 6 months following discontinuation of study treatment.
  - Women who become pregnant or are breastfeeding.
- Request by regulatory agencies for termination of treatment of an individual participant or all participants under the protocol.
- Significant noncompliance with the protocol schedule in the opinion of the investigator.
- The minimum dose of study treatment for Stratum A will be the Dose Level -1 dose, and the lowest dose of study treatment for Stratum B and Stratum C will be the Dose Level -2 dose. Participants who cannot tolerate the lowest Dose Level dose for the specified study Stratum will have study treatment discontinued.

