## 6.0 DOSING DELAYS/DOSE MODIFICATIONS

### Dose modifications for Cabozantinib (XL184)

Toxicities warranting treatment delays and dose modifications, along with supportive care guidelines, are noted below.

Stratum-based dose de-escalation of cabozantinib will be permitted for participants experiencing specified toxicity when treated at a particular dose level, as noted below; reductions will be at one-dose-level increments. In no case will dose de-escalation occur beyond the lowest specified Dose Level dose for a particular Stratum (Dose Level -1 for Stratum A; Dose Level -2 for Stratum B and Stratum C). Dose reductions are permanent. No intra-participant dose escalation will be permitted.

**NOTE: Dose modification during Cycle 1 WILL be permitted.** Participants will be permitted to continue study therapy provided no other criteria for protocol discontinuation apply ([Section 5.4](#)). **HOWEVER, treatment delay of 14 days or longer due to unresolved toxicity during Cycle 1 will require discontinuation of study treatment** ([Section 5.4](#)).

**NOTE:** If a participant experiences several adverse events and there are conflicting recommendations, the investigator should use the recommended dose adjustment that reduces the dose to the lowest level.

**NOTE:** Starting in Cycle 2, if toxicity requiring treatment delay does not resolve in less than or equal to 6 weeks, the study treatment will be discontinued. Treatment delays for other reasons may be permitted at the discretion of the Study Chairs.

Dose De-Escalation Schedule			
Dose Level	Dose of Cabozantinib (XL184)*		
	Stratum A ART Regimens Including Drugs that Inhibit CYP3A4 A (mg/day)	Stratum B ART Regimens Including Drugs that Induce CYP3A4 B (mg/day)	Stratum C All Other ART Regimens C (mg/day)
Level -2	-	20	20
Level -1	20 mg every other day	40	40
Level 1	20	60	60
Level 2	40	100	-
Level 3	60	-	-

\* Cabozantinib (XL184) must be taken whole and on an empty stomach. Participants must fast for 2 hours before and 1 hour following each dose of cabozantinib (XL184). To permit pharmacokinetic sampling studies, AM dosing is required during the first cycle of therapy.

AStratum A: Participants taking either ritonavir-boosted or cobicistat-boosted ART regimens

BStratum B: Participants taking either efavirenz or etravirine-based ART regimens.

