### 8.1 CTEP IND Agent

#### 8.1.1 Cabozantinib (XL184) (NSC 761968)

**Chemical Name:** *N*-{4-[(6,7-dimethoxyquinolin-4-yl)oxy]phenyl}-*N'*-(4-fluorophenyl)cyclopropane-1,1-dicarboxamide, (2S)-hydroxybutanedioate

**Other Names:** Cabozantinib, EXEL-7184, EXEL-02977184

**Classification:** Receptor Tyrosine Kinases Inhibitor (RTK)

**CAS Registry Number:** 1140909-48-3

**Molecular Formula:** C28H24FN3O5.C4H6O5      **M.W.:** 635.6

**Mode of Action:** Cabozantinib inhibits multiple RTKs implicated in tumor growth, metastasis, and angiogenesis, and targets primarily MET and VEGFR2. Other targets are RET, AXL, KIT, TIE-2, and FLT-3.

**How Supplied:** Cabozantinib is supplied by Exelixis and distributed by the DCTD. Cabozantinib is available in 20 mg and 60 mg tablets. The tablets are yellow film coated containing cabozantinib malate equivalent to 20 mg and 60 mg of cabozantinib. The 20 mg tablets have a round shape and the 60 mg tablets have an oval shape, and they are packaged as 30 tablets per bottle.

Cabozantinib should be dispensed in its original container; however, for treatment duration for up to a week, cabozantinib tablets can be dispensed in a pill cup with an expiration date not to exceed 24 hours or in a pharmacy dispensing bottle with expiration date not to exceed 7 days.

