### **9.2 Evaluations During Treatment**

Evaluations may occur within a window of +/- 7 days. Assessments must occur on cycle 1, days 1, 8, 15, and 22, on Cycle 2, days 1 and 15, and on day 1 of all subsequent cycles as indicated in the Schedule of Evaluations ([Appendix I](#)).

- 9.2.1 Complete medical history and physical examination. To include vital signs, weight, performance status, adverse event evaluation). If hypertension (BP 140/90) is observed, decisions to decrease or hold the dose of study treatment must be based on BP readings taken by a medical professional and must be confirmed with a second measurement at least 5 minutes following the first measurement. (Refer to [Section 6.1.8](#) for management.)
- 9.2.2 CBC with differential and platelets, serum chemistry, amylase and lipase, and LFTs defined in [9.1.3](#).
- 9.2.3 Serum TSH. Testing should be performed every 4 weeks (every cycle) beginning Cycle 1 Day 1.
- 9.2.4 PT/INR and PTT. Testing should be performed every 8 weeks (2 cycles) beginning Cycle 1 Day 1.
- 9.2.5 CD4+ and CD8+ lymphocyte counts and HIV viral load. Samples will be obtained locally at time of Pharmacokinetic (PK) Specimen Collection on Cycle 1, Day 22, and at 12 week intervals while on study therapy.
- 9.2.6 Urine dipstick or urinalysis. Proteinuria seen on urine dipstick or UA should warrant urine protein/creatinine ratio (UPCR) determination and management according to [Section 6.1.9](#).
- 9.2.7 ECG and QTc assessments will be performed weekly during the first cycle of therapy, and day 1 of all subsequent cycles. Additional ECGs will be performed as indicated in [Section 6.1.16](#) (refer to [Appendix IX](#) for a list of drugs that may cause QTc prolongation).
- 9.2.8 CT scan for tumor measurement performed after every 2 cycles (every 8 weeks) of therapy for participants with solid tumors. Participants with cutaneous KS will not require CT scans.
- 9.2.9 KS participants will be evaluated for response after every other cycle according to the requirements in [Section 11.2](#). Chest x-ray will be performed as clinically indicated.
- 9.2.10 The participant will be given a copy of the participant diary to complete. Collect diary upon completion.
- 9.2.11 Correlative Studies (See [Section 10.0](#))

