## APPENDIX IV: PHARMACOKINETIC (PK) SPECIMEN COLLECTION, PREPARATION AND SHIPPING INSTRUCTIONS

**To permit pharmacokinetic sampling studies, AM dosing is required during the first cycle of therapy.** Blood for cabozantinib PK assessments should be collected immediately pre-AM dose and 4 hr post-dose on Cycle 1 Day 1. Additional blood sampling for steady-state PK determinations will be collected during the dosing interval at pre-dose (Cycle 1, Day 22), 0.5, 1, 2, 4, 6, 8, and 24 hr (Cycle 1, Day 23). Day 22 and 23 collections will be  $\pm$  1 day. If a participant misses a dose of cabozantinib during Cycle 1 prior to Cycle 1 Days 22/23 and will continue on treatment, [name] should be contacted to determine the optimal timing of the PK collection, which would no longer occur on Cycle 1 Days 22/23. The actual sample collection times should be recorded on a pharmacokinetic worksheet that also documents the time of cabozantinib administration (previous and current dose; along with the use of a participant dosing diary).

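### The Appendix VIII diary can state only daily dosing, so an unedited copy turns Stratum A Level -1 (20 mg on alternate days) into Level 1 (20 mg daily)

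*Combined protocol and SAP*

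**What the plan says.** The dose tables in the Protocol Schema, Section 5.1 and Section 6.0 agree: Stratum A Level 1 is 20 mg daily and Level -1 is "20 mg every other day". The general text of Section 5.1 describes once-daily dosing, but the table in the same section gives the alternate-day exception.

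Level -1 can be reached in two ways. Section 5.1 allows one Stratum A de-escalation cohort at that level if Level 1 proves too toxic. Section 6.0 allows individual reductions for toxicity, and "reductions will be at one-dose-level increments". Section 5.4 makes it the floor: "The minimum dose of study treatment for Stratum A will be the Dose Level -1 dose".

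On supply, Section 8.1.1 states "Cabozantinib is available in 20 mg and 60 mg tablets", and Section 5.1.1 requires tablets to be taken whole.

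Appendix VIII, item 2, instructs dosing "each day in the morning for 4 weeks" and then repeats that the tablets are for every morning. Its only blanks are the two tablet counts. For a missed dose it says "just wait until the next day before taking the next dose". The section completed by the physician's office asks for the planned dose as a daily total and has no field for the dosing interval. The text available for review contains no alternate-day version of the diary and no instruction to amend item 2 for Level -1.

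**The concern.** Section 5.1 asks every participant to keep this diary, which carries a dosing instruction as well as a log. At one dose level that instruction contradicts the dose table, and it errs towards the higher dose. The people affected are those for whom 20 mg daily was too toxic, either individually or as judged from the preceding cohort. Following the form would return them to the dose they were meant to leave.

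There is a smaller risk to the data. If the error went uncorrected in a Level -1 cohort, dose-limiting toxicity and pharmacokinetic results could be credited to half the dose actually taken, in a trial whose primary objective is safety and the maximum tolerated dose.

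**Working it through.** **Inputs.** Tablet strengths of 20 mg and 60 mg, in bottles of 30 (Section 8.1.1); whole tablets only (Section 5.1.1); dose levels from the Section 5.1 table; a 28-day cycle; item 2 as printed.

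**Step 1: which levels can item 2 state?** The form can express 20a + 60b mg every morning, with a and b whole numbers.

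| Dose | Where used | Tablets each morning |
|---|---|---|
| Average 10 mg/day | A Level -1 | none possible |
| 20 mg/day | A Level 1; B and C Level -2 | 1 × 20 |
| 40 mg/day | A Level 2; B and C Level -1 | 2 × 20 |
| 60 mg/day | A Level 3; B and C Level 1 | 1 × 60 or 3 × 20 |
| 100 mg/day | B Level 2 | 2 × 20 + 1 × 60, or 5 × 20 |

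Stratum A Level -1 is the only scheduled level the form cannot state. Entering one 20 mg tablet produces the Level 1 instruction.

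**Step 2: size over a full cycle.**
- Diary: 28 × 20 mg = 560 mg.
- Dose table: 14 × 20 mg = 280 mg.
- Ratio: 560 / 280 = 2.0; excess 14 tablets.

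**Step 3: excess if caught earlier.** The protocol does not say whether alternate-day dosing starts on Day 1 or Day 2, so both are shown.

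| Through day | Diary tablets | Table, odd days | Excess | Table, even days | Excess |
|---|---|---|---|---|---|
| 7 | 7 | 4 | 3 (60 mg) | 3 | 4 (80 mg) |
| 14 | 14 | 7 | 7 (140 mg) | 7 | 7 (140 mg) |
| 21 | 21 | 11 | 10 (200 mg) | 10 | 11 (220 mg) |
| 28 | 28 | 14 | 14 (280 mg) | 14 | 14 (280 mg) |

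In Cycle 1 a check at a Day 8 visit held on time limits the excess to 3 or 4 tablets. Section 9.2 allows ±7 days, and a visit that slips to Day 15 allows 7.

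**Step 4: would existing checks catch it?**
- *Visits.* Cycle 1 has visits on Days 8, 15 and 22. After that they are "on Cycle 2, days 1 and 15, and on day 1 of all subsequent cycles". From Cycle 3, with no other contact, a full cycle (14 excess tablets) could pass before the next scheduled visit.
- *Pharmacokinetic worksheet.* In Cycle 1 it "documents the time of cabozantinib administration (previous and current dose", so consecutive-day dosing would be visible there (Appendix IV).
- *Dispensing.* Section 8.1.2.3 allows short supplies of up to 7 days. A 7-day supply of 4 tablets taken daily runs out after Day 4 and would expose the error. An intact bottle is also allowed, and its 30 tablets cover 28 daily doses.
- *Pill count.* Section 8.1.2.4 sets the count against the diary. For someone who followed the form both show 28, a difference of 0. Only comparison with the assigned schedule reveals the problem.
- *Diary review.* Section 5.1 asks for non-compliance to be noted when the diary is collected. That could catch the error, but only at cycle end.

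**The case against.** The strongest reply is that this is a wording inconsistency on one form, not a flaw in the design. The dose tables agree, and staff know the dose. They must write tablet counts into the very sentence that says every morning, so the error requires them to order alternate-day dosing, complete a sentence that contradicts it, and not explain the change.

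Level -1 may also be rarely reached. Section 5.3.1.3 reports a 38% rise in AUC with a strong CYP3A4 inhibitor in healthy volunteers. Applied to 20 mg this gives 20 × 1.38 = 27.6 mg-equivalent, or 27.6 / 60 = 46% of the 60 mg standard dose. A Level -1 cohort would need at least two dose-limiting toxicities at that exposure. The figure is only indicative, since ritonavir and cobicistat may behave differently.

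Actual intake would also be documented: the log has a row for each day, and the office totals the tablets taken. Under Appendix V the Protocol Chair, Medical Monitor and Group Statistician decide whether dose-escalation or de-escalation criteria are met. Some toxicities that lead to a reduction bring extra contact, such as at least weekly review for hand-foot syndrome (Section 6.1.6) and weekly urine protein monitoring after restart (Section 6.1.9).

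Most of this stands, and it keeps the likelihood low and wrong attribution of data remote. It also means the early-detection counts depend on the starting day and on visit timing. None of it removes the contradiction or the full-cycle factor of 2.0, which depends on neither. Staff vigilance is the only thing separating the printed instruction from the wrong dose.

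**Conclusion.** The point holds, as a minor one. Item 2 cannot state Stratum A Level -1, and with one 20 mg tablet entered it states Level 1 instead. Over a 28-day cycle that is 560 mg against 280 mg, a ratio of 2.0.

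The consequence depends on three conditions: a Stratum A participant at the lowest level, a diary issued without amendment, and no instruction that overrides it. The participant handout and wallet card (Appendix III) and the consent pages were not available, so whether they give the alternate-day schedule is unknown. Confidence is high that the form and the tables conflict; how often this would lead to a wrong dose cannot be estimated from the documents.

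**What to change.** Either add a field to item 2 for daily or alternate-day dosing, or issue a Level -1 diary with the 14 dosing days marked. Reword the missed-dose line so that the participant waits for the next scheduled dosing day. Have the office section record both the planned dose and the schedule, so that tablet totals are checked against the assigned level as well as against the diary.

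The cost is one revised participant form, with no added visits, procedures or participants. Section 14.2 requires a written amendment with CTEP and IRB approval for any protocol change, so the revision can go with the next amendment. Until then, sites with a Stratum A participant at Level -1 can be asked to correct item 2 by hand.
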